# Compare the AIC values of the two models
aic_2par <- AIC(model_2par)
aic_3par <- AIC(model_3par)

# Select the model with the lowest AIC
best_model <- ifelse(aic_2par < aic_3par, "Two-parameter model", "Three-parameter model")

# Compute the ED50 (or T50) from the selected model
if (best_model == "Two-parameter model") {
  ED50 <- ED(model_2par, 50)
} else {
  ED50 <- ED(model_3par, 50)
}
```

After conducting the model fits, we will evaluate the Akaike Information Criterion (AIC) for each model to compare their fit. The model yielding the lowest AIC will be selected as the primary model. From this primary model, we will determine the ED50 (or T50) - the time at which half of the maximum CoNS CFU/cm² is achieved. This approach follows the methodology outlined by Ritz et al., 2015. Adjustments or additional steps may be needed depending on the specifics of the data set and the research question at hand.

The supportive primary analysis will be conducted on the modified intent to treat sample and repeated on the per-protocol sample if it differs from the modified intent to treat sample.

7.4 Secondary Objectives

The secondary objectives are stated below:

1. To assess the duration of survival of CoNS as measured by CFU during a maximum of 24 days after the application of *S. hominis* A9 on non-lesional ventral arm skin of AD participants positive for *S. aureus* (AD SA+).
2. To assess the safety of *S. hominis* A9 or placebo application, as determined by the count of serious and non-serious treatment-emergent adverse events (AEs) during the time period of Day 0 to Day 31 per participant within each group.

7.4.1 Secondary Endpoints

1. The duration of survival, measured as the time needed for CoNS CFU to drop below baseline density measured before application of Sha9 + 100 CFU/cm² on non-lesional ventral arm skin of AD participants positive for *S. aureus* (AD SA+).
2. The count of serious and non-serious treatment-emergent AEs per participant during the time period of Day 0 to Day 31.

7.4.2 Analyses of Secondary Endpoints

Secondary endpoint #1 will be analyzed using the same approach as described for the primary analysis of the primary endpoint (see Section 7.3.2). Median survival time along with 95% CI will be constructed based on a log-log transformed CI for the survivor function $S(t)$. A graph of the Kaplan-Meier survival curve will be presented, and rates at fixed days will be derived (Therneau, et al., 2000). Furthermore, estimation of the hazard rate and 95% CI will be produced using a parametric survival model.

The summary of all treatment-emergent adverse events and treatment-emergent serious adverse events for secondary endpoint #2 will be provided by system organ class, high-level term, and preferred term in descending order of frequency.

Secondary endpoint #1 will be run on the modified intent to treat sample and re-run using the per-protocol sample if this differs from the former. Secondary endpoint #2 will be run on the safety sample.

7.5 Exploratory Objectives

The exploratory objectives are stated below:

1. To assess the association of *S. hominis* A9 estimated CFU on the skin of the ventral arm contralateral to the arm of application and face.
2. To assess the duration of survival of CoNS as measured by CFU during a maximum of 24 days after the application of *S. hominis* A9 on lesional ventral arm skin of AD participants negative for *S. aureus* (AD SA-).
3. To assess the duration of survival of CoNS as measured by CFU during a maximum of 24 days after the application of *S. hominis* A9 on non-lesional ventral arm skin of AD participants negative for *S. aureus* (AD SA-).
4. To compare the duration of survival of CoNS as measured by CFU on lesional skin between AD SA+ vs AD SA- participants.
5. To compare the duration of survival of CoNS as measured by CFU on non-lesional skin between AD SA+ vs AD SA- participants.
6. To compare the duration of survival of CoNS as measured by CFU between lesional and non-lesional skin on AD SA+ participants.
7. To compare the duration of survival of CoNS as measured by CFU between lesional and non-lesional skin on AD SA- participants.
8. To compare disease severity measures (local Eczema Area and Severity Index [L-EASI], SCORing Atopic Dermatitis [SCORAD] and local Pruritus Numerical Rating Scale [NRS]) between Day 0 and the last in-clinic visit among AD SA+ participants, and independently, among AD SA-.
9. To determine the antibiotic sensitivity of the skin CoNS microbiome to penicillin G, tetracycline, and erythromycin before and after treatment with ShA9.

7.5.1 Exploratory Endpoints

1. Association of *S. hominis* A9 bacteria abundance estimated CFU as measured by % *S. hominis* A9 positive colonies by PCR x CoNS CFU while CoNS CFU is above baseline density measured before application of ShA9 + 100 CFU/cm² on the lesional and non-lesional, separately, ventral arm skin of AD participants between the arm treated with *S. hominis* A9 and the contralateral arm treated with placebo, and independently, with the participant's face.
2. The duration of survival, measured as the time needed for CoNS CFU to drop below baseline density measured before application of ShA9 + 100 CFU/cm² on the lesional ventral arm skin of AD participants negative for *S. aureus* (AD SA-).
3. The duration of survival, measured as the time needed for CoNS CFU to drop below baseline density measured before application of ShA9 + 100 CFU/cm² on the non-lesional ventral arm skin of AD participants negative for *S. aureus* (AD SA-).

4. Comparison of time needed for CoNS CFU to drop below baseline density measured before application of ShA9 + 100 CFU/cm² on the lesional and non-lesional, separately, ventral arm skin between AD participants positive (AD SA+) vs negative (AD SA-) for *S. aureus*.
5. Comparison of time needed for CoNS CFU to drop below baseline density measured before application of ShA9 + 100 CFU/cm² on lesional vs non-lesional skin of AD participants positive (AD SA+) and negative (AD SA-) for *S. aureus*, separately.
6. Comparison of the L-EASI score of the ventral arms at Day 0 vs the last in-clinic visit among AD SA+, and independently, among AD SA-.
7. Comparison of the SCORAD score at Day 0 vs the last in-clinic visit among AD SA+, and independently, among AD SA-.
8. Comparison of the local Pruritus NRS of the ventral arms at Day 0 vs the last in-clinic visit among AD SA+, and independently, among AD SA-.
9. Comparison of the proportion of antibiotic-sensitive CoNS to penicillin G, tetracycline, and erythromycin isolated from skin swabs at baseline and after ShA9 treatment, at the last swab collection from lesional skin.

7.5.2 Analyses of the Exploratory Endpoints

Repeated measures correlation will be calculated for determining the common within-individual association for paired (*S. hominis* treated arm and contralateral arm treated with placebo, and independently, with the participant's face) for *S. hominis* A9 bacteria abundance estimated CFU as measured by % *S. hominis* A9 positive colonies by PCR x CoNS CFU assessed on two or more days. The correlation coefficient, the 95% confidence interval, and the p-value will be reported. Log transformation will likely be needed for the outcome of interest to produce a less skewed distribution (Bland and Altman, 1995).

Analyses of disease severity (L-EASI, SCORAD, and local Pruritus NRS) change between Day 0 vs the last in-clinic visit among AD SA+, and independently, among AD SA- will be conducted using a repeated measures mixed-effects model with an unstructured covariance matrix. The model will estimate the pre-intervention vs. post-intervention least squares mean \pm standard error and the difference reported with a 95% confidence interval and p-value.

Analyses to investigate if ShA9 application can change CoNS antibiotic sensitivity to penicillin G, tetracycline, and erythromycin will be conducted on all participants (AD SA+ and AD SA-) by comparing the proportion of antibiotic-sensitive CoNS [(CFU without antibiotic containing plate - CFU with antibiotic containing plate) / CFU without antibiotic containing plate] before and after treatment. We will model the difference in proportions of antibiotic-sensitive CoNS between swabs taken at baseline and swabs taken at the last Follow-Up Visit.

The exploratory analyses will be conducted on the modified intent-to-treat sample, and due to the exploratory nature of this endpoint analysis, no adjustments will be made for multiple comparisons.

8. SAFETY EVALUATION

8.1 Overview of Safety Analysis Methods

All safety analyses will be carried out using the safety sample. Missing safety information will not be imputed. Listings will be prepared for all safety measurements. All listings will be sorted in order of S.

aureus positive/*S. aureus* negative status, participant identifier, and the time of assessment (e.g., visit, time, and/or event).

8.2 Adverse Events

All AEs will be classified by system organ class (SOC) and preferred term, according to a standardized thesaurus (Medical Dictionary for Regulatory Activities [MedDRA] version 25.0).

Each AE is entered on the eCRF once at the highest severity. As such, no additional data manipulation is needed to identify events.

AEs will be collected from the time of consent until the participant completes study participation or until 30 days after he/she prematurely withdraws (without withdrawing consent) or is withdrawn from the study. Treatment-emergent AEs are defined as new AEs or an increase in grade of an AE after investigational product application (Day 0).

An overall summary table will be developed to report the number of events and the number and percentage of participants having at least one event in the following categories:

- AEs
- AEs indicated as serious
- AEs with an outcome of death
- AEs that were reported as being related to the study treatment
- AEs reported by maximum severity

In addition, AEs classified by MedDRA SOC, and preferred term will be summarized by arm dominance and overall, for each of the following:

- All AEs
- AEs by maximum severity
- AEs by relationship to study treatment

Summary tables will present the total number of events as well as the number and percentage of participants experiencing the events. If a participant experiences the same AE on multiple occasions, the event will be counted once for each occurrence when reporting the number of AEs. When reporting the number of participants experiencing the events, a participant will only be counted once if he/she experiences an event within the particular SOC or preferred term.

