3.5. Stratification, Randomization, and Blinding/Masking

Arm dominance may affect the spread of ShA9 to the contralateral arm; therefore, the design will stratify by arm dominance, with the dominant arm being the right arm for right-handed participants, and the left arm for left-handed participants. A minimum of 13 participants with *S. aureus* colonized lesions on their ventral arms and a minimum of 7 participants with *S. aureus* negative lesions on their ventral arms will be randomized to one of two treatment groups: 1) ShA9 dominant and placebo non-dominant or 2) ShA9 non-dominant and placebo dominant. It is anticipated that enrollment will be higher for right-handed participants as that is the more dominant arm in the general population; enrollment will not target equal numbers of right-handed and left-handed participants. Randomization will be performed centrally at the Statistical and Clinical Coordinating Center (SACCC) using a stratified randomization design.

This is an open-label study, as all participants will receive active and placebo treatment. However, investigators, all investigational site staff, including those responsible for preparing/administering the investigational product, and all participants in this study will be blinded as to which arm received which treatment. Laboratory staff performing the mechanistic assays will be unblinded to which arm received which treatment, to ensure the correct dilutions can be applied to each sample prior to completing assays for quantification of live bacteria by culture (*S. aureus* and CoNS) and bacterial DNA (*S. hominis* A9) by qPCR (Refer to [Section 9](#)).

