13.4.4 Analyses of Secondary Endpoints

Overall survival comparisons between culture-positive and culture-negative for *S. aureus* colonization will be performed using a two-sided log-rank test with a significance level of 10%. Additionally, if the log-rank test is significant, the hazard ratio (HR) along with the 95% CI will be reported from a Cox proportional hazards regression model (discrete/exact method).

The summary of all treatment-emergent adverse events and treatment-emergent serious adverse events will be provided by system organ class, high-level term, and preferred term in descending order of frequency, and by preferred term in descending order of frequency. All analyses for adverse events will be conducted for the safety population by *S. hominis* A9 and Placebo.

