8.3 Deaths and Serious Adverse Events

Serious adverse events (SAEs) will be listed and summarized in the same manner described in Section 8.2. Separate displays listing and summarizing death, including time to death and cause of death, will also be created.

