12. CHANGES TO THE ANALYSES PLANNED IN THE PROTOCOL

A per-protocol (pp) analysis sample not originally defined in the protocol has been added to the statistical analysis plan.

The planned analysis for secondary endpoint #1 described in Section 13.4.4 of the Protocol does not correctly describe an appropriate analysis plan for that endpoint. Section 7.4.2 of the SAP has been updated to correctly describe the intended planned analysis for secondary endpoint #1.

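### The protocol (Version 2.0) analyses adverse events by ShA9 and placebo; the SAP text tabulates them by arm dominance, which cannot show that contrast, and does not list the change

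*SAP*

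**What the plan says.** Protocol 13.4.4 ends its safety paragraph with "All analyses for adverse events will be conducted for the safety population by" S. hominis A9 and Placebo. The split is therefore by product.

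The SAP is laid out differently:

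- **8.2:** "In addition, AEs classified by MedDRA SOC, and preferred term will be summarized by arm dominance and overall". The overall AE summary table that comes before this has no grouping.
- **8.3:** serious AEs "will be listed and summarized in the same manner described in Section 8.2".
- **7.4.2:** the summary "for secondary endpoint #2 will be provided by system organ class, high-level term, and preferred term in descending order of frequency", with no product or other group named.
- **8.1:** listings are sorted by S. aureus status, participant and time; arm and product are not in the sort order.
- **12:** two changes are listed. One is "A per-protocol (pp) analysis sample not originally defined in the protocol has been added to the statistical analysis plan". The other opens "The planned analysis for secondary endpoint #1 described in Section 13.4.4 of the Protocol does not correctly describe" and concerns that endpoint only. AEs are not mentioned, although the AE sentence sits in the same protocol section.

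The SAP keeps the secondary safety objective (7.4), which covers application of ShA9 or placebo and counts events "during the time period of Day 0 to Day 31 per participant within each group". Protocol 3.5 defines the randomised groups as "1) ShA9 dominant and placebo non-dominant or 2) ShA9 non-dominant and placebo dominant".

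**The concern.** The placebo arm is the within-person control (protocol 4.1), and the AE count is a secondary endpoint. If the analysis follows the SAP text alone, no table compares events on ShA9-treated skin with events on placebo-treated skin.

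The comparison matters because some local reactions are expected from both products. Protocol 5.1 names contact dermatitis to glycerol as a theoretical risk of either one, and skin infection as a theoretical risk of applying ShA9. The same preferred term on one arm or the other would be counted identically. The tables by relationship to study treatment in SAP 8.2 do not fill the gap, because relationship is a causality judgement and not a record of which product was on the skin. Culture of a suspected infection (protocol 8.7) addresses bacterial cause case by case, and only if swabs are taken.

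**Working it through.** **Step 1. Compare the texts.**

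| Item | Protocol V2.0, 13.4.4 | SAP |
|---|---|---|
| AE tables | ShA9 and placebo | Arm dominance and overall (8.2) |
| Serious AEs | Covered by the same sentence | As 8.2 (8.3) |
| Secondary endpoint #2 | Covered by the same sentence | No grouping named (7.4.2) |
| Change recorded | n/a | No (12) |

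**Step 2. Ask what arm dominance could mean as a column.** The SAP does not define it for AE tables. Section 5.1 ties it to handedness; 10.2 uses it as a group label. There are three readings:

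- *Handedness (right versus left).* Every participant in either column has both products.
- *Randomised group.* The two groups in protocol 3.5 are mirror images, and each contains both products.
- *Dominant versus non-dominant arm.* Each column mixes ShA9-treated and placebo-treated arms across participants.

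The first two readings show no ShA9-versus-placebo contrast at all. Randomised group crossed with the arm of the event would recover the product, but the SAP does not describe that crossing.

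**Step 3. How much survives under the third reading.** Let a be the event risk on the ShA9 arm, b the risk on the placebo arm (neither depending on dominance), and p the share of participants with ShA9 on the dominant arm.

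- Dominant arm: p·a + (1 − p)·b
- Non-dominant arm: (1 − p)·a + p·b
- Difference: (2p − 1)(a − b)

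The planned minimum is 20 participants. The allocation ratio is not stated, so the splits below are assumed.

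| ShA9 dominant : non-dominant | p | Share of a − b retained |
|---|---|---|
| 10:10 | 0.50 | 0% |
| 11:9 | 0.55 | 10% |
| 12:8 | 0.60 | 20% |
| 14:6 | 0.70 | 40% |

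If fewer than half have ShA9 on the dominant arm, the sign reverses.

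**Step 4. Worked example (assumed counts, 10:10 split).** Four participants have a local reaction on the ShA9 arm, two in each randomised group. None has one on the placebo arm.

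- By product: 4/20 versus 0/20.
- By randomised group: 2/10 versus 2/10.
- By dominant versus non-dominant arm: 2/20 versus 2/20. The two dominant-arm events come from the ShA9-dominant group and the two non-dominant-arm events from the other group.

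**Step 5. Precision of the by-product table.** Exact (Clopper-Pearson) 95% intervals are 5.7% to 43.7% for 4/20 and 0% to 16.8% for 0/20, the latter bound being 1 − 0.025^(1/20) = 0.168. With an assumed 25 participants and no events the upper bound is 1 − 0.025^(1/25) = 0.137. These are separate intervals for each arm; they do not use the pairing.

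**The case against.** Five points can be made for the SAP.

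1. **Version.** The SAP's synopsis is of Protocol Version 3.0; the protocol supplied is Version 2.0. Section 12 need only list departures from the version in force, and its AE sentence has not been seen. This stands as a limit: an unlisted departure from Version 3.0 is not proven.
2. **Table specifications.** SAP Section 2 places them in separate documents, and a product split could be there. This also stands, so the finding is confined to the SAP text.
3. **The SAP may be the coherent document.** The endpoint counts events per participant, each participant has both products, and the phrase about groups in the objective could mean the two randomised groups. A by-product count requires each AE to be assigned to an arm, and neither document gives a rule. It is fair that the protocol sentence could be the one to change. But the objective concerns ShA9 or placebo application, and protocol 13.4.4 names the products, so the conflict has to be settled either way.
4. **The (2p − 1) result covers one reading only.** That reading fits poorly with tables of participant counts and percentages. True, but the other readings show no product contrast at all.
5. **Limited harm.** This is a small pilot. Staff record dispenser ID and arm (protocol 6.1.1.2.3 and 6.1.2.2.3), arm codes can be opened for clinically significant events (3.5.1), and the stopping rules act on single related events (11.5). These protect individual participants but do not supply the by-product tabulation.

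**Conclusion.** The concern holds. On the texts supplied, the SAP replaces a by-product AE analysis with one by arm dominance and does not say so. Under two readings of arm dominance the ShA9-versus-placebo contrast is absent. Under the third, between 0% and 40% of it remains for splits from 10:10 to 14:6 in a sample of 20.

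The textual conflict needs no assumption. The percentages rest on assumed splits and on event risks that do not depend on dominance; the worked example also rests on assumed counts. Confidence is medium, because Protocol Version 3.0 and the table specifications are unseen. The point should be fixed, but a by-product table from about 20 pairs would be descriptive: even zero events in 20 is compatible with a risk of up to 16.8%.

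**What to change.** 1. Check the AE sentence in Protocol Version 3.0 and the separate table specifications.
2. If the product split is still intended, amend SAP 7.4.2, 8.2 and 8.3 to tabulate treatment-emergent AEs in three columns (ShA9 arm, placebo arm, not arm-specific), plus the existing overall column. Give participant counts with exact 95% intervals and no test.
3. State how an AE is assigned to an arm, and make sure the side of each local AE is recorded. The documents do not say whether it is.
4. If arm dominance stays as a column, define it.
5. If the product split is not intended, record and justify the change in SAP Section 12.

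The cost is SAP text and table shells, plus one item on the AE form if side is not already collected. The table needs the arm codes, so it belongs to the final analysis, after the written NIAID approval for unblinding in protocol 3.5.1. Its limits should be stated alongside it: systemic AEs cannot be assigned to an arm, spread of ShA9 to the placebo arm may dilute the contrast, and the estimates will be imprecise.

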8.3 Deaths and Serious Adverse Events

Serious adverse events (SAEs) will be listed and summarized in the same manner described in Section 8.2. Separate displays listing and summarizing death, including time to death and cause of death, will also be created.

8.4 Vital Signs, Physical Findings, and Other Observations Related to Safety

8.4.1 Vital Signs

Data listings sorted by *S. aureus* positive/*S. aureus* negative participant status, vital sign parameter, and the time of assessment will be provided for vital sign measurements. Vital signs include systolic blood pressure (mmHg), diastolic blood pressure (mmHg), heart rate (bpm), respiratory rate (respirations/min), temperature (F), height (in), weight (lbs), and body surface area (m²).

8.4.2 Pregnancy Assessment

Pregnancy tests (urine) will be performed on female participants of child-bearing potential who do not self-report as pregnant at the Screening (Day -14 to Day -7) and Treatment (Day 0) visits. If a female participant becomes pregnant prior to the Treatment Visit (Day 0), the participant will no longer be

eligible to participate in the study and will be withdrawn from all future study activities listed in the Schedule of Events.

At all other study visits, female participants of child-bearing potential will be asked if they are pregnant. If a pregnancy occurs, the pregnant participant will continue all study activities listed in the Schedule of Events. All pregnancies identified during the study shall be followed to conclusion and reported in a listing by participant. If pregnancy complications result in a congenital abnormality, birth defect, miscarriage, or medically indicated abortion, an SAE shall be reported.

